### 4.3 WITHDRAWAL CRITERIA

Patients will be withdrawn from the study in the following situations:

- Disease progression (IWCLL 2008 criteria)
- o Adverse events: a patient may be removed from the study following a severe (grade 3) or life-threatening (grade 4) adverse event at the discretion of the treating physician
- Withdrawal of consent by the patient
- Major protocol deviations (i.e., non-compliance with treatment procedures)
- Investigator's decision
- Sponsor's decision if an inacceptable toxicity observed in another patient led the Safety Committee to recommend a transient or permanent discontinuation of the study

After treatment withdrawal, patients will be followed for at least 4 weeks after last study drug administration or until recovery from all related adverse events to grade 1 or less, or until the toxicity level is stable for at least 6 weeks (except in case of consent withdrawal - see below). The patient will then complete the End of Study (EOS) visit.

After the EOS visit, information on the survival of the patients will be collected periodically by the sponsor through contact with the investigator. In addition, appropriate alternative treatment will be proposed by the investigator to the withdrawn patient.

CONFIDENTIAL

Release date: Edition number

GED version

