# 4.3.1 Data Collection for withdrawal patient

In case of premature discontinuation from the study for any reason (except in case of withdrawal of consent), the investigator must make every effort to perform the end of study assessments. These data should be recorded in the medical record and eCRF, as they consist of an essential evaluation that should be done prior to withdrawing any patient from the study.

The primary reason for withdrawal will be clearly documented in the patient's medical record and recorded in the eCRF.

If a patient has a premature treatment discontinuation, the treating physician will contact the patient every 3 months for 3 years as part of the post-study follow-up. Patients will be followed until they die or withdraw consent for contact in which case the date of death will be determined from public records (e.g. the Social Security database or publications).

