3.2.3 Both phases

In both phases, treatment by monalizumab will be limited to 56 weeks, or less, in the event that a complete response with undetectable MRD is documented for 2 months. Treatment by ibrutinib will be at least administered until the end of the study follow-up period (up to 12 months after end of monalizumab treatment), unless disease progression (International Workshop on Chronic Lymphocytic Leukemia (IWCLL)), untoward toxicity, or consent withdrawal leads to the premature interruption of the ibrutinib treatment.

[figure not shown]
Page 8 of 26

TPL N°: eTPL SA-02-01 Of SOP SA-02.08 TPL Effective Date: 31 Mar 2016 TPL Version: 02
Approved in Vault: 3/8/2019

Patients will be enrolled for a post study follow-up enabling the investigator to document disease progression (IWCLL) or death, for 3 additional years after the completion of their in study follow-up.

The following figure illustrates the treatment schedule in both phases:

EOT: End of Treatment; EOS: End of Study

TPL Effective Date: 31 Mar 2016 Approved in Vault: 3/8/2019

The schedule of assessments is shown in Table 1 and Table 2.

Table 1

PHASE I Flow-chart	Screening ³	W0 C1	W0D2 C1	W0D8 C1	W2 C2	W2D2 C2	W4 C3	W4D2 C3	W4D8 C3	W6 C4	W6D2	W8 to W52 C5 to C16	EOT ⁹ W56	FU1 to FU7 ¹⁵	EOS ¹²
Informed consent	X												- 8	8	A S
Inclusion / Exclusion criteria	X	X											- 3		36
Demography, Medical history	X							370.00							
Concomitant illness	X	X	X	X	X	X	X	X	X	X	X	X	X	X	X
Concomitant medication	X	X	Х	X	X	X	Х	Х	X	Х	Х	X	X	X	Х
Tumor assessment ¹⁴	X						X		- 3			X	X	X	X
IPH2201 administration		Х			Х		Х		001-0	X		X			
Ibrutinib administration ²							х	X	X.	Х	х	Х	Х	X	
Safety assessments													3		
Weight	X	X			X		X			X		X	X	X	X
Height	X														
Physical examination ⁴	X	X			X		X			X		X	X	X	X
Vital signs	X	X	X	X	X	X	X	X	Х	X	X	X	X	X	X
ECOG status	X	X			X		X			X	100	. X	X	X	X
Adverse events	-330	X	X	Х	X	X	X	X	X	X	X	X	X	X	X
12-lead ECG ¹¹	X	X	9 9	1					3	X		W16, W32	3		X
Laboratory assessments															
Hematology ⁵	X	X	Х	X	X	X	X	Х	X	X	X	X	X	X	X
Biochemistry ⁶	x	X	х	х	х	×	х	x	х	x	x	W8, W16, W24, W32 W40,W48	×	FU3, FU5, FU6, FU7	×
Coagulation factors ⁸	X						X					W8	X		
Thyroid gland'	X		8 8						- 3			1	3	ě.	X
Urinalysis ¹⁰	X						X					W32	X		s = 5001
Pregnancy test	1,000	X													X
HIV / HBV / HCV screen	X		18 8							- 1		3	- 8	5	8.8
Beta 2 microglobulin	X		10 3										- 3		9
Serum Ig ¹³	X											W16, W32	X		

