- 8) Coagulation factors: activated partial thromboplastin time (APTT), prothrombin time (PT). at Screening, at predose of W4 and W8, and at EOT

TPL Version: 02

9) EOT visit to be performed in case of premature discontinuation - or 14 days +3 days after W52 visit.

Page 10 of 26

TPL N°: eTPL SA-02-01 Of SOP SA-02.08

Version: 2.0

- 10) Urinalysis: PH, Glucose, Leucocytes, proteins, blood and hemoglobin, to be performed at screening, in predose of W4 and W32 visits and at EOT
- 11) 12-lead ECG should be performed at screening, W0 predose, W0 H0+3 +/ 1 hour, in predose of W6, W16, W32 visits and at EOS
- 12) End of study visit to be performed in case of premature discontinuation, or at the end of the follow up, +/ -7 days after previous visit
- 13) Testing for IgG, IgM, IgA and total immunoglobulin levels at screening, in predose of W16 and W32 visits and at EOT.
- 14) Tumor Assessment: pretreatment tumor assessment should be performed within 3 weeks before the first dose. Tumor assessments by physical examination should be performed at W4, W8; afterwards at all visits until EOS. A CT scan (with contrast unless contraindicated) of the chest, abdomen, and pelvis is required for the pretreatment tumor assessment. New CT-scan should be performed at W4 visit, at W16 visit, at EOS, and to confirm any CR or progression.
- 15) Follow up visits, after EOT and during 12 months: follow-up visits FU1 to FU4 to be performed monthly and hereafter follow-up visits FU5 2 months after FU4, FU6 and FU7 to be performed every 3 months.
- 16) Receptor Saturation Assay: to be performed at Screening visit for baseline value; for patients in phase 1b part, at W0 H0 (predose), and H0+3 (2 hours after end of IPH2201 infusion); W0D2; EOT; FU1 to FU7 and at EOS
- 17) For patients in phase 1b part, PK assessments at W0 H0 (pre-dose), H0+1 (end of IPH2201 infusion) and H0+3 (2 hours after end of IPH2201 infusion); W0D2 (24 hours after end of IPH2201 infusion, +/- 6 hours); W0D8 W2 at H0 (pre-dose), H0+1 and H0+3; W4 at H0 (pre-dose), H0+1 and H0+3; W4D2; W4D8; W6, W12, W20, W28, W36, W14 and W52 visits, at H0 and H0+1; at EOT, FU1 to FU7 and EOS
- 18) NK & T cell markers and immunophenotyping sampling is to be performed at predose of W0, W0D2, W4, W4D2, W28 visits; at EOT a nd at EOS.
- 19) Include detection of genetic abnormalities usually associated to CLL, IgVh mutational status and ZAP 70 methylation profile

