8.4 Remission with undetectable MRD

Undetectable MRD is defined as the percentage of CLL cells of all lymphocytes below 0.01%. The rate of patients in cCR at W52 with undetectable MRD in peripheral blood and bone marrow will be summarized overall and by dose level, and the 95% confidence interval for this rate will be calculated only overall for the patients in the phase Ib and for the patients in the phase IIa. Remission with undetectable MRD needs to be confirmed, i.e. CR and undetectable MRD should be met jointly and confirmed jointly. The rate of remission with undetectable MRD in peripheral blood and in bone marrow will be displayed separately.

8.5 Duration of Remission (DOR), Duration of Complete Remission (DOCR), Progression free Survival (PFS) and Overall Survival (OS)

The duration of Remission (DOR) and duration of complete Remission (DOCR) will be assessed in the main endpoint population, whereas the Progression Free Survival (PFS) and Overall Survival (OS) will be assessed in the ITT/safety population.

The DOR, for the remission assessed at 52 weeks, is defined as the time from the date of first evaluation of the remission (CR or PR) to the first documentation of progressive disease, relapsed disease or death. In case an assessment of a progressive disease, relapsed disease or death record does not exist, the duration of remission is censored at the time of the last disease assessment date. The duration of remission is only calculated for the patients with a cCR, an uCR or a PR assessed at 52 weeks.

The DOCR is calculated similarly for the patients with a cCR assessed at 52 weeks.

The PFS is defined as the time from first dose administration until the occurrence of progressive disease, relapsed disease or death from any cause. Patients without an event at the time of the analysis will be censored at his or her last disease assessment date; patient with no post-baseline assessments will be censored at the day of first dose administration.

The OS is defined as the time from first dose administration until death from any cause. Alive Patients are censored at the most recent date they are known to be alive. Subjects with no assessment post-baseline will be censored at the day of first dose administration.

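### SAP 8.5 sets no time limit on PFS, DOR and DOCR events but censors event-free patients at the last disease assessment, which biases Kaplan-Meier down after EOS if post-study events are counted

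*SAP*

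**What the plan says.** **Events.** SAP 8.5: "The PFS is defined as the time from first dose administration until the occurrence of progressive disease, relapsed disease or death from any cause". It gives no cut-off at EOS and no limit on the time since the last assessment. DOR ends at progression, relapse or death, again without a limit, and DOCR is calculated in the same way.

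**Censoring.** For PFS: "Patients without an event at the time of the analysis will be censored at his or her last disease assessment date". For DOR: "the duration of remission is censored at the time of the last disease assessment date". For OS the rule differs: "Alive Patients are censored at the most recent date they are known to be alive".

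**When disease is assessed.** The flow-chart footnotes say: "Tumor assessments by physical examination should be performed at W4, W8; afterwards at all visits until EOS". Under Protocol 3.4, treatment lasts up to 56 weeks in phase Ib and 52 weeks in phase IIa, with 12 months of follow-up after IPH2201. EOS therefore falls at about month 24 to 25.

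**What is collected afterwards.** SAP 3.2.3: "Patients will be enrolled for a post study follow-up enabling the investigator to document disease progression (IWCLL) or death, for 3 additional years" after in-study follow-up ends. Protocol 4.3, on withdrawn patients: "After the EOS visit, information on the survival of the patients will be collected periodically by the sponsor through contact with the investigator". Protocol 4.3.1 adds contact every 3 months for 3 years after premature treatment discontinuation. If a patient withdraws consent for contact, it continues: "in which case the date of death will be determined from public records". No tumor assessment is scheduled after EOS.

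**Output.** SAP 8.5 plots Kaplan-Meier curves for DOR, PFS and OS. It names medians with confidence intervals for DOR and DOCR only.

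**The concern.** Kaplan-Meier requires that being followed past a given time does not depend on whether an event is coming. As SAP 8.5 is worded, a patient who progresses or dies after EOS is carried to the event date. A patient seen to be well over the same period is put back to the last disease assessment. After EOS the risk set then consists almost entirely of patients who will have an event, so each late event removes a large fraction of the curve. OS escapes this because alive patients are censored at last known alive. That contrast also shows that the SAP treats last contact and last disease assessment as different dates.

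At stake are PFS, DOR and DOCR, the endpoints that describe how long benefit lasts. Two programmers could also produce very different curves from the same data, depending on how they treat a post-study contact.

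**Working it through.** **Plan's own figure.** No precision or event calculation is given for PFS or DOR. The one design calculation (SAP 3.3.2: 27 patients, positive with at least 4 CRs, rates 0.05 and 0.20) reproduces: exact one-sided alpha is 0.0437 and power 0.818. It does not depend on the censoring rule.

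**Calendar.** The first visit was planned for 9 November 2015 (protocol synopsis). Adding 56 weeks and 12 months puts the earliest phase Ib EOS in December 2017, about 15 months before the SAP approval stamp of 8 March 2019. Post-study data could therefore exist at the analysis. From the first visit to the end of 1Q 2019, the planned last visit, is just under 41 months, so no patient could have a month-48 or month-60 value by then.

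**Hand case (invented counts).** Kaplan-Meier is S(t) = product of (1 - d/n) over event times. Take 27 patients: 6 events by month 24, 2 post-study events at months 28 and 33, and 19 event-free.

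| Time | Event-free patients censored at EOS | Event-free patients followed past month 33 |
|---|---|---|
| Month 24 | 21/27 = 0.778 | 21/27 = 0.778 |
| Month 28 | 0.778 x (1 - 1/2) = 0.389 | 0.778 x (1 - 1/21) = 0.741 |
| Month 33 | 0.389 x (1 - 1/1) = 0 | 0.741 x (1 - 1/20) = 19/27 = 0.704 |

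The patients and events are the same in both columns; only the censoring date differs.

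**Simulation inputs.**
- n = 27 (SAP 3.3.2).
- Hazard -ln(0.75)/26 = 0.0111 per month, from the ibrutinib-alone PFS of 75% at 26 months in Protocol 1.1.5.1. Applying it here, and the exponential form, are assumptions.
- EOS at about month 24.2 and uniform accrual over 18 months (Protocol 3.4).
- No early dropout, analysis at the last patient's EOS, 4,000 runs.

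True PFS is exp(-0.0111t): 0.77, 0.72 and 0.67 at months 24, 30 and 36. There are about 2.0 post-EOS events per trial on average.

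| Rule | Month 24 | Month 30 | Month 36 | Curve ends at 0 |
|---|---|---|---|---|
| Late events counted, event-free patients censored at EOS | 0.77 | 0.40 | 0.18 | 86% of runs |
| Late events counted, event-free patients censored at last known progression-free date | 0.77 | 0.72 | 0.67 | 1% of runs |
| Events and censoring both stopped at EOS | 0.77 | no estimate | no estimate | 0% of runs |

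Repeat runs gave 0.18 to 0.19 at month 36 and a curve ending at zero in 83 to 86% of runs.

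**Sensitivity to the hazard.** At half the hazard, the first rule gives 0.55 and 0.33 at months 30 and 36 (true 0.85 and 0.82), with 70% of runs ending at zero. At double the hazard it gives 0.27 and 0.09 (true 0.51 and 0.45), with 95% ending at zero.

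**Early leavers.** Suppose 10, 20 or 30% of patients stop assessments in months 2 to 12 while their events are still captured. The month-24 estimate is then 0.759, 0.748 or 0.734 against 0.767, a small bias.

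**The case against.** The strongest reply is that the SAP says last disease assessment and does not restrict it to in-study visits. Post-study follow-up exists to document IWCLL progression. Under Protocol 7.2.2 that rests on nodes, spleen, liver, blood counts and histology, so documenting it implies some assessment. If event-free post-study checks are recorded as assessments, censoring moves forward with them and the bias disappears, as in the second row of the simulation table. The SAP also does not say that post-study data enter this analysis at all. Both points stand, and they make the problem conditional. They do not settle it, because the documents schedule no assessment after EOS and describe part of that period as contact or survival information only.

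It is also fair that PFS and DOR are secondary, descriptive endpoints in a single-arm trial, that individual values are listed, and that the hazard comes from relapsed or refractory patients while this trial also enrols untreated ones.

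Four stronger readings are tempting, and the documents do not support them:
- **The curve must fall to zero.** This needs post-study data in the analysis and an event after the last censoring time. It is likely under the assumptions above, but not certain.
- **Month-48 or month-60 estimates are badly wrong.** Under the planned calendar, no such follow-up exists for a 2019 analysis.
- **The reported PFS median will be too short.** No PFS median is planned.
- **Withdrawn patients yield survival data only.** Protocol 3.5.1 also collects progression after discontinuation for safety.

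**Conclusion.** The point holds in conditional form. SAP 8.5 gives events and censoring different observation windows. If post-study events are counted and event-free post-study contacts are not treated as disease assessments, Kaplan-Meier PFS is biased down after EOS. The illustrative size is about 0.40 against 0.72 at month 30 and 0.18 to 0.19 against 0.67 at month 36. This rests on the assumed hazard, exponential form, accrual pattern and analysis date; the direction does not depend on those values.

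DOR and DOCR carry the same rule, so their curves and planned medians are exposed in the same direction; their size was not calculated. The curve to about month 24 is essentially unaffected without early dropout. The primary decision (at least 4 CRs in 27) is unaffected. The change should be made before analysis, but it does not threaten the trial's main conclusion.

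**What to change.** In SAP 8.5, define last disease assessment, state whether post-study data enter PFS, DOR and DOCR, and apply one observation window to events and censoring.

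- **Preferred.** If post-study events count, censor event-free patients at the last date documented alive and progression-free, including post-study contacts that check progression. A contact that establishes survival only should not extend this date. This keeps Protocol 7.2.3's PFS definition, which counts death without a time limit, and uses the 3-year follow-up.
- **Alternative or sensitivity analysis.** Stop both events and censoring at EOS, or count events only up to a fixed interval after the last disease assessment. That interval should match each phase's visit schedule, because follow-up is monthly at first in phase Ib and every 3 months in phase IIa.

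The cost is a few sentences of SAP wording and one date derivation, with no new visits or patients. The preferred option needs the progression check and its date to be recorded at post-study contacts. Under the alternative, later events leave that analysis and the curve stops near EOS.

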# 7.2.4 Overall survival (OS)

OS is defined as the time from study entry until death from any cause, and is measured in the intent-to-treat population.

[figure not shown]

CONFIDENTIAL

Release date: Edition number 12 August 2016

GED version

MOD-3783

[figure not shown]

Release date: Edition number

GED version

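### The SAP's OS rule for subjects with no post-baseline assessment makes no exception for death or known survival, so read literally it censors a known death at first dose

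*SAP*

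**What the plan says.** SAP section 8.5 gives OS three sentences. The event: "The OS is defined as the time from first dose administration until death from any cause". The censoring of survivors: "Alive Patients are censored at the most recent date they are known to be alive". Then a free-standing third sentence: "Subjects with no assessment post-baseline will be censored at the day of first dose administration". None of them says which assessment is meant.

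The PFS paragraph just before is built differently. Its event runs "until the occurrence of progressive disease, relapsed disease or death from any cause". Its censoring sentence opens "Patients without an event at the time of the analysis will be censored at his or her last disease assessment date" and continues after a semicolon: "patient with no post-baseline assessments will be censored at the day of first dose administration".

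The protocol attaches no assessment condition to OS. Section 7.2.4 states: "OS is defined as the time from study entry until death from any cause, and is measured in the intent-to-treat population". Survival is also followed outside study visits. Section 4.3 has the sponsor collect it through the investigator after the End of Study visit. Section 4.3.1 has patients who stop treatment early contacted every 3 months for 3 years and, for those who withdraw consent for contact, adds: "in which case the date of death will be determined from public records".

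**The concern.** The first two OS sentences already cover every patient: the dead are events, and the living are censored when last known alive. The third has no condition on vital status, so a programmer who follows it to the letter overrides both. A patient who died without a post-baseline assessment becomes a day-1 censoring. A patient known from later contact to be alive, but never assessed, contributes no time at risk.

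What is at stake is the OS curve and the event count printed on it. For deaths the error runs in one direction, in favour of the treatment. The report could also contradict itself, with fewer OS events on the Kaplan-Meier graph than deaths in the safety table.

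**Working it through.** **The plan's own figures.** The documents give no planned OS or PFS value, so there is none to reproduce. The one design calculation is the phase IIa rule in SAP 3.3.2: 27 patients, positive with at least 4 complete remissions, null rate 0.05, alternative 0.20. Exact binomial: P(X ≥ 4 | 27, 0.05) = 0.0437 and P(X ≥ 4 | 27, 0.20) = 0.8177. This agrees with the stated one-sided 0.05 and 80% power. The rule counts remissions only, so OS censoring does not enter it.

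**The three OS sentences applied to patients with no post-baseline assessment.**

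| Patient | First two sentences | Third sentence, literally |
|---|---|---|
| Known to have died | Event at date of death | Censored at first dose |
| Known alive at a later date | Censored at that date | Censored at first dose |
| Nothing known after first dose | Censored at first dose, the last date known alive | Censored at first dose |

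The third sentence adds nothing in the last row and conflicts with the first two sentences in the other rows.

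**Who can fall under it.** The window depends on the undefined word.
- If any visit counts, the first is W0D2, 24 hours ± 6 hours after first dose (Protocol 6.2.1.1 and 6.2.2.1). Few or no patients would be exposed.
- If only disease assessments count, the first scheduled one is at W4 (Protocol 7.2 and flow-chart footnote 14).
- Even then, the End of Treatment and End of Study visits held on premature discontinuation each require a tumor assessment by physical examination (Protocol 6.3 and 6.5). Most early withdrawals should therefore have one. Those left are mainly early deaths and early withdrawals of consent.

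**Size for deaths.** Let N be the patients analysed, k the deaths with no post-baseline assessment and d the other deaths, with no other censoring. The documents give neither k nor d, so both are assumptions. N = 27 is the planned efficacy number and N = 45 the stated maximum for the trial.

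- Literal rule: S = 1 − d/(N − k)
- Deaths counted: S = 1 − (k + d)/N

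| N | k | d | Literal | Counted | Gap, points |
|---|---|---|---|---|---|
| 27 | 0 | any | same | same | 0 |
| 27 | 1 | 0 | 1.000 | 26/27 = 0.963 | 3.7 |
| 27 | 1 | 2 | 24/26 = 0.923 | 24/27 = 0.889 | 3.4 |
| 27 | 1 | 5 | 21/26 = 0.808 | 21/27 = 0.778 | 3.0 |
| 27 | 2 | 0 | 1.000 | 25/27 = 0.926 | 7.4 |
| 27 | 3 | 0 | 1.000 | 24/27 = 0.889 | 11.1 |
| 45 | 1 | 0 | 1.000 | 44/45 = 0.978 | 2.2 |

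**Direction for survivors.** Censoring a living patient at day 1 removes no event and shrinks the risk set. With N = 27, two deaths and one such survivor, the literal rule gives 1 − 2/26 = 0.923, against 1 − 2/27 = 0.926 if that survivor is followed throughout. The estimate falls by 0.3 points. With no deaths it is unchanged. Only unassessed deaths push OS upward.

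**The case against.** The strongest reply is that the third sentence is a fallback for patients about whom nothing further is known, since reading it as cancelling the event definition makes the paragraph contradict itself. That may well be the intention, but the sentence does not say so. The two sentences before it already handle that case, and a SAP is programmed from its wording.

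It can also be said that the window may be only a day. The protocol does use the word assessment for vital signs, laboratory tests and adverse events, and the no-assessment clauses do not say disease. This stands as a limit on size. The only assessment named in the neighbouring duration-of-remission and PFS rules is the disease assessment, so the W4 reading is possible but not established. Eligibility also requires a life expectancy of at least 3 months, which makes a count of zero plausible.

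A reader might infer more than the documents support:
- **That PFS loses early deaths too.** It does not. The PFS clause sits in a sentence that opens with patients without an event, and death is a PFS event, so an early death stays an event.
- **That early leavers as a group inflate OS.** Those known to be alive leave the estimate unchanged or lower it, and most early withdrawals should have a tumor assessment anyway.
- **That public-record death dates are discarded in general.** They are lost only for patients who also had no post-baseline assessment.
- **That deaths vanish from the report.** SAP 9.4 tabulates and lists deaths with cause, and SAP 9.3 tabulates fatal treatment-emergent events.

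**Conclusion.** The concern holds for OS alone, as a rule that gives a wrong result when followed literally. It conflicts with the SAP's own OS definition, with its last-known-alive rule and with Protocol 7.2.4.

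The size is conditional. Each unassessed death removes one OS event. A single such death raises the estimate by 3.0 to 3.7 points with 27 patients and 0 to 5 other deaths, and by 2.2 points with 45 patients and no other deaths, assuming no other censoring. The number of such deaths is not given and may be zero, in which case OS is not biased upward at all.

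OS is a secondary, descriptive endpoint, shown as a Kaplan-Meier graph with event counts; SAP 8.5 plans medians only for the two remission durations. Neither the sample size nor the threshold of 4 remissions in 27 depends on it. The sentence should still be corrected, because a survival analysis should not censor a known death and the section should not hold two incompatible rules.

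**What to change.** In SAP 8.5, delete the third OS sentence, or limit it to patients with no vital-status information after first dose. State that every death is an OS event at its date whatever assessments exist, and that all other patients are censored at the last date known alive, including dates from follow-up contact and public records.

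For PFS, repeating the words without an event in the clause after the semicolon, and naming the disease assessment, is an optional clarification and not a correction.

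The cost is one sentence in the SAP, or two with the PFS clarification. No patients, visits or data are added, because the protocol already collects the survival information.
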